8.2. Study Population and Setting

Strimvelis is indicated for the treatment of patients with ADA-SCID, for whom no suitable human leukocyte antigen (HLA)-matched related stem cell donor is available. A registry study (PRJ2684/200195) will be implemented with long-term prospective, non-interventional follow-up of the safety and effectiveness of Strimvelis. Patients in the registry will be monitored for at least 15 years post-treatment with Strimvelis.

Parents/carers and referring HCPs of patients enrolled within this registry will be contacted separately and asked to participate in their respective surveys evaluating the effectiveness of risk minimisation measures. The survey will be conducted via telephone interviews in the local languages for parents/carers and for referring HCPs. Parent/Carers and referring HCPs survey are distinct and results will not be linked for confidentiality reasons.

In order to be considered eligible to participate in the study, HCPs will be required to meet the following criteria:

- HCPs or HCPs' close family members may not have been employees of GlaxoSmithKline, Pharmaceutical Product Development, LLC (PPD), the Food and Drug Administration (FDA), or the European Medicines Agency (EMA).
- HCPs must be licensed.
- An HCP must not have previously completed a survey regarding Strimvelis educational materials.
- An HCP must have previously referred a patient for Strimvelis treatment.

In order to be considered eligible to participate in the Parent/Carer survey, parents or carers will be required to meet the following criteria:

 Parents/carers or parents'/carers' close family members may not have been employees of GlaxoSmithKline, Pharmaceutical Product Development, LLC (PPD), the Food and Drug Administration (FDA), or the European Medicines Agency (EMA).

- A parent/carer must not have previously completed a survey regarding Strimvelis educational materials
- A parent's or carer's child must have previously received treatment with Strimvelis.

The study will recruit for approximately two years until 10 referring HCPs and 10 parents/carers have completed their respective surveys (length of study may vary contingent upon product uptake).

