8.3.3. Outcome definitions

This study will assess the proportion of parents/carers and referring HCPs at six months post treatment with Strimvelis that understood the possible risks relating to:

Safety concerns (KRM topics):

- 1. Malignancy due to insertional oncogenesis (e.g. leukaemia, myelodysplasia)
- 2. Autoimmunity
- 3. Unsuccessful response to gene therapy
- 4. Pregnancy

Other areas of interest:

- Requirement for long-term monitoring
- Receipt of the patient treatment alert card

The proportion of parents/carers and referring HCPs who acknowledge receipt of routine and additional risk minimization measures (e.g., SmPC/PIL, educational materials, Patient Alert Card) will be assessed as a measure of implementation.

The type of medical specialty and experience of referring HCPs will be summarized.

The primary outcome of these surveys is the proportion of parents/caregivers and referring HCPs that provide correct responses to a series of questions concerning the specific risks associated with Strimvelis.

Sufficient understanding of a key risk message can be assumed if at least 80% or more respondents correctly answer all questions that are included within that particular key risk message [ISPE White Paper 2016].

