8.5. Study size

All parents/carers and referring HCPs from patients enrolled in the Strimvelis product registry will be invited to complete the surveys. The study will recruit for approximately two years until 10 referring HCPs and 10 parents/carers have completed their respective surveys (length of study may vary contingent upon product uptake).

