8.6. Data management

A user-friendly Internet-based survey tool with an intuitive interface will be employed to manage data in this survey. Parents/carers, who have agreed that they may be contacted about such future studies, will be contacted by the Gene Therapy Registry Centre (GTRC). Questions will be asked to the parents/carers and HCPs and responses to the survey entered by the GTRC. Surveys for both parents/carers and HCPs will be entered via an electronic data collection system by the local interviewer.

In order to minimize bias, the survey instruments will include the following design features:

- Response options for multiple-choice questions will be randomized, where appropriate.
- Participants will be asked by the interviewer to answer all questions.

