5. You should report any concerning signs or	a. True		
symptoms that you	b. False		

Survey Question	Answer	N	%
notice after your child is treated with Strimvelis to your child's specialist doctor.	c. I don't know		
KRM 1: Gene therapy f	or ADA-SCID and risk of	of blood cancer (e.g. leu	ikaemia)
6. Your child's specialist doctor will	a. True		
check your child's blood for any signs of	b. False		
leukaemia during check-ups.	c. I don't know		
7. Within the last last 6 months, has your child	a. Yes		
been seen by their specialist doctor for	b. No		
follow-up after receiving Strimvelis?	c. I don't know		
If you answered "Yes," approximately how many times have you seen your child's specialist doctor?			
If you answered "Yes,"has your child	a. Yes		
given blood samples at least once within the	b. No		
last 6 months?	c. I don't know		
8. How often should your child be followed	a. At least once a year		
up by his or her specialist doctor?	b. Every 5 years		
	c. Every 10 years		
KRM 2: Autoimmunity			
9. Autoimmunity occurs when the body's	a. True		
immune system sees its own tissues and cells as	b. False		
foreign and attacks these healthy cells.	c. I don't know		
Symptoms may include a high temperature,			

Survey Question	Answer	N	0/0
rash, joint pain, painful or weak muscles, or feeling tired or unwell most of the time. If you are concerned about autoimmunity, you should contact your specialist doctor.			
10. Autoimmunity can occur (select all that apply):	a. Before treatment because of the disease b. After treatment as the immune system is restored		
	c. Both		
KRM 3: Unsuccessful re	esponse to gene therapy		,
11. Gene therapy is designed to treat the	a. True		
immune issues of ADA-SCID, including	b. False		
frequent severe infections.	c. I don't know		
12. Gene therapy is designed to treat non-	a. True		
immune issues such as fatty liver, reduced	b. False		
hearing, or behavioural problems.	c. I don't know		
13. Immune and non- immune issues will be	a. True		
followed up during routine visits by your	b. False		
child's specialist doctor.	c. I don't know		
14. Symptoms such as fever, cough, loose	a. True		
stools, pain on passing urine may suggest	b. False		
infection and should be reported to your specialist doctor	c. I don't know		

Survey Question	Answer	N	0/0
KRM 4: Pregnancy			
15. Strimvelis is not designed to correct the	a. True		
genetic defect in your child's reproductive	b. False		
cells.	c. I don't know		

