Please answer based on your knowledge of Strimvelis as informed by the Strimvelis Educational Materials, including the product Summary of Product Characteristics (Product Label).
3. Strimvelis is recommended as first-line therapy for any patient affected by ADA-SCID.
Please select one response.
a. True
b. False
c. I don't know
4. Strimvelis is indicated for the treatment of patients with severe combined immunodeficiency due to ADA deficiency, for whom no suitable HLA matched related stem cell donor is available.
Please select one response.
a. True
b. False
c. I don't know
5. Strimvelis is contraindicated in patients with a history of previous gene therapy.
Please select one response.
a. True
b. False

c. I don't know

CONFIDENTIAL

WWEpi Project number: PRJ2678/205881

6. Patients eligible to receive treatment with Strimvelis should have a bone marrow harvest for stem cell back-up at least 3 weeks prior to treatment with Strimvelis. Please select one response. a. True b. False c. I don't know 7. Parents and carers of patients receiving treatment with Strimvelis should be educated on the fact that the patient should not be able to donate blood, organs, tissues, or cells for transplantation. Please select one response. a. True b. False c. I don't know 8. It is recommended that patients treated with Strimvelis are regularly followed up clinically (at least annually). Please select one response. a. True b. False c. I don't know 9. Strimvelis is contraindicated in patients with a current or previous history of leukaemia or myelodysplasia. [KRM 1] Please select one response. a. True b. False

c. I don't know

CONFIDENTIAL

WWEpi Project number: PRJ2678/205881

10. Have you given advice to parents/carers/patients regarding monitoring for signs and symptoms of leukaemia? [KRM1] Please select one response. a. Yes b. No c. I don't know 11. Have you performed blood tests (including red blood cell indices, white blood cell count differential, platelet count, and a routine biochemistry screen) within the first year of a patient's returning from treatment with Strimvelis? [KRM1] Please select one response. a. Yes b. No c. I don't know 12. Regular monitoring for clinical autoimmunity (possibly including tests for auto-antibodies) is recommended. [KRM2] Please select one response. a. True b. False c. I don't know 13. Autoimmunity may be observed during immune reconstitution after gene therapy. [KRM2] Please select one response. a. True b. False

b. No

c. I don't know

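### In three key risk messages (HCP KRM 1, HCP KRM 2, parent KRM 4) every item is evidently correct when answered True or Yes, so a respondent who merely agrees passes

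*Protocol*

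**What the plan says.** Protocol 8.3.3 sets the success rule for each message: "Sufficient understanding of a key risk message can be assumed if at least 80% or more respondents correctly answer all questions" belonging to it. Section 8.5 recruits "until 10 referring HCPs and 10 parents/carers have completed their respective surveys", so 8 correct respondents out of 10 are needed in each survey. On mode, section 8.2 states: "The survey will be conducted via telephone interviews in the local languages for parents/carers and for referring HCPs".

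Annex 4 tags HCP Q9-11 as KRM 1 and Q12-13 as KRM 2. Q9 reads "9. Strimvelis is contraindicated in patients with a current or previous history of leukaemia or myelodysplasia. [KRM 1". Q10 and Q11 ask whether the HCP has given advice on leukaemia monitoring and has done blood tests. Q12 reads "12. Regular monitoring for clinical autoimmunity (possibly including tests for auto-antibodies) is recommended. [KRM2" and Q13 "13. Autoimmunity may be observed during immune reconstitution after gene therapy. [KRM2". In Annex 2, Table 7, parent KRM 4 consists of Q15 (the product is not meant to correct the defect in reproductive cells) and Q16 (family planning advice at a suitable age).

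The measures against bias are a fixed question order with no going back (8.3.4) and, in 8.6, "Response options for multiple-choice questions will be randomized, where appropriate". Section 8.9 names interviewer-led questioning as a possible bias and offers no remedy for it. Agreement with statements as such is not mentioned.

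**The concern.** A True/False item separates knowledge from agreement only if agreeing is sometimes wrong. Where every item in a message is keyed True or Yes, a respondent who knows the content and one who goes along with the interviewer give the same answers within that message. Under an all-correct rule both pass, and no later analysis of that message can tell them apart. HCP KRM 1 and KRM 2 cover malignancy and autoimmunity, two of the four safety concerns the study is meant to evaluate, and the results go to the regulator as evidence on the risk minimisation measures.

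HCP Q10 and Q11 add to this. They ask about the HCP's own conduct, so a socially desirable Yes is scored as understanding. Q9 is then the only knowledge item in HCP KRM 1.

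**Working it through.** **Step 1: key each KRM item.** No answer key stands in the protocol body, in Annex 2, or in Annex 4 as far as HCP Q13. The rest of Annex 4 and Annex 5 were not available for this check. HCP Q14-20 and the parent items are therefore read from the Annex 2 table shells, and the key is inferred from the wording.

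| Survey, message | Items | True/Yes | False | Multi-option | Passed by agreement alone? |
|---|---|---|---|---|---|
| HCP KRM 1 | Q9-11 | 3 | 0 | 0 | Yes |
| HCP KRM 2 | Q12-13 | 2 | 0 | 0 | Yes |
| HCP KRM 3 | Q14-18 | 4 | 0 | 1 (Q16) | Not outright |
| HCP KRM 4 | Q19-20 | 1 | 1 (Q19) | 0 | No, it fails |
| Parent KRM 1 | Q6-8 | 2 | 0 | 1 (Q8) | Not outright |
| Parent KRM 2 | Q9-10 | 1 | 0 | 1 (Q10) | Not outright |
| Parent KRM 3 | Q11-14 | 3 | 1 (Q12) | 0 | No, it fails |
| Parent KRM 4 | Q15-16 | 2 | 0 | 0 | Yes |

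Three of eight combinations are passed by agreement alone. Over both surveys, 10 + 8 = 18 of 12 + 11 = 23 KRM items are keyed True or Yes (78%). Table 4 groups HCP Q6-11 under malignancy instead of Q9-11. The three added items also read as True, so HCP KRM 1 stays one-sided under either grouping.

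**Step 2: effect on the 80% rule.** The protocol derives no figure for this, so there is none to reproduce. Let u be the share who would get the whole message right from knowledge, and a the share of the remainder who agree by default. In a one-sided message the pass probability is p = u + (1 - u)a. The chance of meeting the rule is

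P(X ≥ 8) = 45p⁸(1 - p)² + 10p⁹(1 - p) + p¹⁰, with X ~ Bin(10, p).

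Both u and a are assumptions; the documents give neither. With u = 0.60:

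| a | p | P(at least 8 of 10) |
|---|---|---|
| 0 | 0.60 | 0.167 |
| 0.10 | 0.60 + 0.40 × 0.10 = 0.64 | 0.241 |
| 0.25 | 0.60 + 0.40 × 0.25 = 0.70 | 0.383 |
| 0.50 | 0.60 + 0.40 × 0.50 = 0.80 | 0.678 |

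The direction does not depend on these values: p ≥ u for any a ≥ 0.

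**Step 3: effect of one reversed item.** Respondents who agree by default now fail the message, so p returns to u = 0.60 and the chance to 0.167. If the agreeing habit also overrides knowledge in a share a of all respondents, p falls to (1 - a)u. With a = 0.10 that is 0.54, and the chance is 0.089. A reversed item therefore removes the upward error and can introduce a downward one.

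**Step 4: do the stated controls act here?** Fixed order and no going back stop later items from revealing earlier answers. Randomised option order acts on a preference for the first or last option. Neither touches agreement with a statement's content. The option of not knowing, offered on these items, helps only with respondents who admit that they do not know.

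**The case against.** The strongest reply is that the surveys already contain checks. HCP Q19 and parent Q12 are evidently False, and so are HCP Q3 and parent Q4 outside the messages. Section 8.7.1 tabulates every question as correct or incorrect, so blanket agreement would show up as failures on those items, even with 10 respondents. This stands as a diagnostic for the survey as a whole. It does not change the pass or fail of a message that has no such item, because 8.3.3 scores each message on its own items.

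A reader might infer three stronger things that the documents do not support:

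- That nearly all messages can be passed by agreement, since 10 of 11 HCP and 8 of 9 parent two-way KRM items are keyed True or Yes. The all-correct rule means that one False or multi-option item is enough to break this, and five of the eight combinations have one.
- That the error always favours finding the measures effective. In HCP KRM 4 and parent KRM 3 an agreeing respondent fails, so the error there runs the other way.
- That near-truisms such as parent Q14 ("14. Symptoms such as fever, cough, loose" stools and so on, to be reported) or HCP Q20 make the case. Both sit in messages that already hold a False item.

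It is also fair that the agreement rates are assumed, that licensed referring HCPs may agree by default less often than parents, and that the surveys are reported descriptively. At a = 0.10 the change from 0.167 to 0.241 is modest.

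**Conclusion.** The point holds for HCP KRM 1, HCP KRM 2 and parent KRM 4 only. In these, agreement alone passes the message, and default agreement can only raise the pass rate. Its size cannot be established from the documents; the 0.17 to 0.68 range at 60% understanding is an illustration under assumed agreement rates of 0 to one half. The conclusion rests on an inferred key, which is plain for parent Q15-16 and HCP Q9, Q12 and Q13. For HCP Q10-11 it assumes that Yes is scored as correct.

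The protocol itself shows that reversal is feasible. HCP Q19 puts as a false statement the same fact that parent Q15 puts as a true one, so the same agreeing behaviour fails the HCP pregnancy message and passes the parent one. This is a cheap improvement to the instrument rather than a fault that invalidates the study.

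**What to change.** Before launch, reword one knowledge item in each of the three messages as a short, plausible false statement without a negation, keeping the tested fact unchanged:

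- **HCP KRM 1:** Q9. Q10 and Q11 ask about behaviour and cannot be reversed. The wording should be drawn from the product label, which is not part of the protocol.
- **HCP KRM 2:** Q13, for example 'Autoimmunity occurs only before gene therapy'.
- **Parent KRM 4:** Q15 with its negative removed, so that it mirrors HCP Q19.

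Carry the changes into Annexes 2, 4 and 5. The sample size, the 80% rule and the other messages stay as they are. The cost is retranslating three items and a small risk that a reversed item is misheard by telephone, which is why the statements should be short and free of negatives. The readability review already planned in 8.8 can cover the new wording.
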